#### Safety Follow-Up Period

Safety follow up for subjects not entering the OLE will consist of 1 required visit, 30 days after the last IMP intake (Week 23 or sooner in case of early discontinuation) including an echocardiogram. An additional follow-up echocardiogram will be performed at 6 months ( $\pm 1$  month) after the last IMP intake only for subjects exposed to IMP for more than 3 weeks.

For subjects continuing to the OLE study:

#### Conversion Period (3 weeks)

The 3-week Conversion Period will be required for subjects who choose to enroll in the OLE study at the end of the Maintenance Period. Doses for subjects participating in the 3-week Conversion Period will be gradually adapted (increased or decreased) in a blinded way to reach the entry dose for the OLE. Subjects who took placebo during the maintenance phase will progressively receive PSL.

### **2.6.2 Study duration per subject**

The total duration of study per subject will be up to 27 weeks with a maximum of 19 weeks exposure to PSL. An additional follow-up echocardiogram will be performed at 6 months ( $\pm 1$  month) after the last IMP intake only for subjects exposed to IMP for more than 3 weeks and either discontinuing the study or not entering the OLE.

The end of the study is defined as the date of the last SFU Visit (30-days after the last IMP intake) of the last subject in the study. Additionally, the reporting of SAEs will continue until the 6-month follow-up echocardiogram.

### **2.6.3 Treatments to be administered**

All IMP will be administered in a double-blind manner.

All subjects will be instructed to take 5 or 6 tablets containing either PSL or placebo bid, approximately 12h apart. The IMP should be dosed within 30 minutes after food when practically feasible.

Subjects will be allocated to 1 of the following 5 treatment arms using the IRT system at the Randomization Visit (Visit 2):

- Padsevonil 100mg/day (or 50mg bid)
- Padsevonil 200mg/day (or 100mg bid)
- Padsevonil 400mg/day (or 200mg bid)
- Padsevonil 800mg/day (or 400mg bid)
- Placebo

**Table 2-1: Schedule of assessments**

		BL Period (4 Wk)	Treatment Period (16 Wk ±1 week from Visit 2)								Taper/Conversion Period (3 to 4 Wk ±1 week) a		SFU (30 days after IMP intake)	Unsch Visit b
			Titration Period (3 Wk ±1 week) (±3 days per week)			Stab (1 Wk ±3 days)	Maintenance Period (12 Wk ±1 week) (±3 days per week)							
Visits	V1	V2 BL	TC	V3	TC	V4	V5	V6	V7 (EDV/EOT)	TC	V8	V9		
Assessments	Start of Week x	Wk -4	D 1	Wk 1	Wk 2	Wk 3	Wk 4	Wk 8	Wk 12	Wk 16		Wk 19/20	Wk 23	
Written informed consent		X												
Call IRT to obtain subject number and dispensation of Subject Trial Card		X												
Demographic data		X												
Verification of inclusion/exclusion criteria		X	X											
Verification of withdrawal criteria			X	X	X		X	X	X	X				
General medical/procedures history		X												
Epilepsy history including etiology, diagnosis, surgery, and seizure history		X												
Documentation of MRI (within 10 years)		X												
Documentation of video-EEG		X												
AED history		X												
Habits and lifestyle		X												
Randomization (IRT)			X											
C-SSRS Baseline c		X												

**Table 2-1: Schedule of assessments**

		BL Period (4 Wk)	Treatment Period (16 Wk ±1 week from Visit 2)								Taper/Conversion Period (3 to 4 Wk ±1 week) a		SFU (30 days after IMP intake)	Unsch Visit b
			Titration Period (3 Wk ±1 week) (±3 days per week)			Stab (1 Wk ±3 days)	Maintenance Period (12 Wk ±1 week) (±3 days per week)							
Visits	V1	V2 BL	TC	V3	TC	V4	V5	V6	V7 (EDV/EOT)	TC	V8	V9		
Assessments	Start of Week x	Wk -4	D 1	Wk 1	Wk 2	Wk 3	Wk 4	Wk 8	Wk 12	Wk 16		Wk 19/20	Wk 23	
C-SSRS since last visit c,d			X		X		X	X	X	X		X	X	
HADS c			X				X			X			X	
SSG c			X				X			X			X	
QOLIE-31-P c			X				X			X			X	
CIWA-B c										X		X	X	
Vital signs e	X	X		X			X	X	X	X		X	X	
Body weight and height f	X	X					X	X	X	X		X	X	
Physical examination g (XF = Full – XB = Brief)	XF	XB					XB			XF		XF	XB	
Neurological examination h (XF = Full – XB = Brief)	XF	XB					XB			XF		XF	XB	
Psychiatric and Mental Status		X		X			X	X	X	X		X	X	
12-lead ECG i	X	X		X			X	X		X		X	X	
Echocardiogram j	X								X				X k	
Blood/urine sample for clinical laboratory analyses	X	X					X		X	X		X	X	
Blood sample for concomitant AED assay l,m	X	X							X	X				
Blood sample for PSL PK analysis n,m				X			X	X	X	X				

**Table 2-1: Schedule of assessments**

		BL Period (4 Wk)	Treatment Period (16 Wk ±1 week from Visit 2)								Taper/Conversion Period (3 to 4 Wk ±1 week) a		SFU (30 days after IMP intake)	Unsch Visit b
			Titration Period (3 Wk ±1 week) (±3 days per week)			Stab (1 Wk ±3 days)	Maintenance Period (12 Wk ±1 week) (±3 days per week)							
Visits		V1	V2 BL	TC	V3	TC	V4	V5	V6	V7 (EDV/EOT)	TC	V8	V9	
Assessments	Start of Week x	Wk -4	D 1	Wk 1	Wk 2	Wk 3	Wk 4	Wk 8	Wk 12	Wk 16		Wk 19/20	Wk 23	
Blood sample for DNA			X											
Blood sample for RNA			X				X			X				
Blood sample for proteins/lipids/metabolites			X				X			X				
Pregnancy test o		X	X		X		X	X	X	X		X	X	
Seizure evaluation (count & type) p			X	X	X	X	X	X	X	X	X	X	X	
Concomitant medications (AEDs and non-AEDs) and procedures		X	X	X	X	X	X	X	X	X	X	X	X	
Recording of adverse events		X	X	X	X	X	X	X	X	X	X	X	X	
Health-related outcomes and HRU		X	X		X		X	X	X	X		X	X	
IMP dispensing (IRT)			X		X		X	X	X	X				
IMP accountability and return q					X		X	X	X	X		X		
Entry and exit personal outcome interview r		X								X				
Study termination												X	X s	

AED=antiepileptic drug; BL=Baseline; BP=blood pressure; CIWA-B=Clinical Institute Withdrawal Assessment-Benzodiazepines; C-SSRS=Columbia-Suicide Severity Rating Scale; DNA=deoxyribonucleic acid; ECG=electrocardiogram; EDV=Early discontinuation Visit; EEG=electroencephalogram; ; HADS=Hospital Anxiety and Depression Scale; HRU=healthcare resource utilization; IMP=investigative medicinal product; IRT=interactive response technology; MRI=magnetic resonance imaging; OLE=open-label extension; PK=pharmacokinetic; PSL=padsevonil; QOLIE-31-P=Quality of Life Inventory in Epilepsy-31-P; RNA= ribonucleic acid; SFU=Safety Follow-Up; SSG=Seizure Severity Global Item; Stab=Stabilization Period; TC=telephone call; Unsch=unscheduled; V=visit; Wk=Week

a Taper Period, for subjects who choose to not enter OLE study EP0093, will last for 3 weeks plus 1 week of drug-free period. Conversion Period, for subjects who choose to enter OLE study EP0093, will last for 3 weeks.

b At any time, the subject may have an additional study visit if the Investigator or the subject and/or legal representative deem it necessary. Appropriate assessments will be conducted in relation to the reason for the visit.

c Questionnaires to be completed by all subjects prior to any other study procedures at the visit, when possible.

d If an unscheduled visit is conducted due to safety or efficacy reasons, a C-SSRS assessment will be performed with the subject during the visit. If an unscheduled visit is conducted for reasons other than safety or efficacy concerns (eg, replacement of lost medication, repeated collection of a laboratory specimen due to collection, or analysis issues), a C-SSRS will not be required at these visits.

e Vital signs measured in supine position after 5 minutes of rest include pulse rate, respiratory rate, systolic BP, and diastolic BP.

f Height will only be measured at Visit 1.

g Full physical examinations will assess cardiac and respiratory function via auscultation and review of the following body systems: general appearance; ear, nose, and throat; eyes; hair and skin; respiratory; cardiovascular; gastrointestinal; musculoskeletal; hepatic; neurological; and mental status. Brief physical examinations will include a review of the following body systems: general appearance (including mental status); skin; respiratory; cardiovascular; gastrointestinal; and hepatic.

h Brief neurological examination will include a general assessment and evaluation of reflexes, muscle strength and coordination, and cerebellar function. Full neurological examinations will include in addition, evaluation of cranial nerves, motor system (general muscle strength and tone), sensations in upper/lower extremities.

i Baseline ECG has to be scheduled and results received before Visit 2. An ECG at the SFU Visit will be performed only if abnormal at end of treatment or premature discontinuation visit. All ECG recordings will be performed with the subject resting in the supine position for at least 5 minutes.

j The echocardiogram will be conducted at Visit 1. Echocardiograms will be repeated at Visit 6 for subjects continuing the OLE study. Subjects discontinuing will have an echocardiogram 30 days after last IMP intake at the SFU Visit (except if performed at Visit 6). A repeat echocardiogram will be performed for subjects with a new finding, Grade 2 (moderate severity), or Grade 3 (severe severity).

k An echocardiogram will also be performed 6 months after last IMP intake for subjects exposed to >3 weeks to IMP and discontinuing the study (but not for subjects with <3 weeks exposure).

l AED samples will ideally be taken immediately prior to dose of concomitant medication on each occasion. If this is not possible, then the sample may be taken at any time after dose and the timing of sample in relation to dose should be kept the same ( $\pm 1$  hour) on each occasion for each subject. Therefore, the timing of visits for each subject when AED samples are collected should be scheduled approximately at the same time whenever possible. Assay of parent PSL and metabolites may be included in the AED panel of tests at Visits 6 and 7.

m On Visits 6 and 7, unless the concomitant AED sample is within  $\pm 5$  minutes of a scheduled MITRA sample for PSL assay, a separate, additional MITRA sample will be taken at same time as the concomitant AED blood sample.

n Subjects are requested to provide blood samples for measurement of PSL and metabolites whenever possible. On Visits 3, 5, and 6, site personnel should obtain blood samples for measurement of random PSL concentrations at any time between IMP intake and record accurately the time of last IMP intake and the time of sample collection. On Visits 4 and 7, blood samples for measurement of sparse PK profiles will be collected as follows: immediately before IMP intake

---

(maximum 15 minutes before intake) and then 3 times after (between 30 minutes and 3 hours after IMP intake), taken at least 30 minutes apart. All samples may be taken either at home or in the site or partly at home and partly at the site.

o For all female subjects, serum pregnancy test at Visits 1 and 7 (in case the subject enters into the OLE study) and where applicable, Urine pregnancy test will be used at other visits for female subjects of childbearing potential.

p Seizure counts are collected on the subject's daily record card on a daily basis.

[figure not shown]
q At each visit following an IMP dispensation, IMP should be presented to check for compliance.

r Subject entry interview will be performed on a voluntary basis either at Visit 1 or Visit 2. Subject/caregiver exit interview/survey will be performed on a voluntary basis either at Visit 6 or Visit 7.

s The SFU Visit will be performed only for subjects who do not enter EP0093.

REDACTED COPY  
This document cannot be used to support any marketing authorization application and any extensions or variations thereof.

**Figure 2–1: Study design**

## 2.7 Determination of sample size

The sample size was calculated based on achieving 90% power to observe a statistically significant result for either the 400mg bid and 200mg bid or 200mg bid and 100mg bid doses when compared to placebo, for a change from Baseline of the log-transformed ( $\ln x + 1$ ) 28-day adjusted seizure frequency. Multiplicity is controlled for using the Hochberg step up procedure.

The log-reduction from Baseline in seizure frequency was assumed to be 0.195 for placebo and 0.492, 0.670, 0.754, and 0.780 for the 50mg bid, 100mg bid, 200mg bid, and 400mg bid doses of PSL, respectively. A common SD of 0.985 was assumed. These estimates are based on prior experience in epilepsy together with the EP0069 study results.

With power of 90%, a 2-sided Type-1 error of 5%, and all dose groups of the same size, 80 subjects are required per arm, giving a total of 400 subjects.

Assuming a screening failure rate of approximately 20%, it is anticipated to enroll around 500 subjects and randomize 400 subjects in this study.

The study is also powered to give over 80% power to observe a statistically significant result for the 75% response rate. For the 75% responder rate, assumptions were a 0.121 responder rate for placebo and corresponding responder rates of 0.233, 0.301, 0.332, and 0.342 for the 50mg bid, 100mg bid, 200mg bid, and 400mg bid doses of PSL, respectively.

## 3 DATA ANALYSIS CONSIDERATIONS

### 3.1 General presentation of summaries and analyses

Statistical analysis and generation of tables, figures, subject data listings, and statistical output will be performed using SAS Version 9.3 or higher. All tables and listings will use Courier New font size 9.

Descriptive statistics will be displayed to provide an overview of the study results. For categorical variables, the number and percentage of subjects in each category will be presented. Unless otherwise noted, all percentages will be displayed to 1 decimal place. No percentage will be displayed for zero counts, and no decimal will be presented when the percentage is 100%. For continuous variables, descriptive statistics will include number of subjects with available measurements (n), mean, SD, median, minimum, and maximum.

Decimal places for descriptive statistics will always apply the following rules:

- “n” will be an integer
- Mean, SD, and median will use one additional decimal place compared to the original data
- Minimum and maximum will have the same number of decimal places as the original value.

Unless otherwise specified, statistical tests of efficacy variables will be presented as two-sided p values rounded to three decimal places. P-values less than 0.001 will be presented as “<0.001” and p-values greater than 0.999 will be presented as “>0.999.” Statistical comparisons will be two-sided and will be performed at the 0.05 level of significance.

A complete set of data listings containing all documented data as well as calculated data (e.g., change from Baseline), as applicable, will be generated.

Treatment groups will be displayed as: Placebo, PSL 50 mg bid, PSL 100mg bid, PSL 200mg bid, and PSL 400mg bid.

Log-transformation is based on natural logarithm. For analyses on log-transformed values, model estimates will be back-transformed to anti-log space for table presentation. See Section 8.1.1 for details.

Data collected at scheduled visits will be included the by-visit summary. Data collected at unscheduled visits will not be included in the by-visit summary, but will be considered when determining the Last Visit, minimum, and maximum post-Baseline values during the Treatment Period. Data collected on Visit 8 will be summarized separately for subjects in the Conversion Period versus the Taper and Safety FU Period.

In general, all CRF data will be presented in the subject listings.

## **3.2 General study level definitions**

### **3.2.1 Initial processing of diary data for seizure frequency**

Subjects are instructed to record in their diary all types of seizures that occur, after each seizure or at least once a day. The investigator will assess and confirm the seizures according to the ILAE codes (ILAE Classification of Epileptic Seizures, 1981) and record the seizure types and frequency in the eCRF/diary. With regard to cluster seizures, investigators are to report the number of cluster episodes rather than reporting the estimated number of individual seizures.

### **3.2.2 Analysis time points**

#### **3.2.2.1 Relative day**

Study day for each subject is calculated relative to the date of the first administration of study drug. The date format in the study is dd-MMM-yyyy. Relative day is calculated as the current date in the study minus the date of first dose of study drug for days prior to the first dose of study drug, and the current date minus the date of first dose of study drug plus 1 for days on or after the day of first dose of study drug and prior to or on the day of last study drug dose (e.g., the day of first dose will be Day 1 and the day prior to first dose will be Day -1). For days after the last dose of study drug, relative day will be calculated as the current date minus the date of last dose of study drug and including a "+" to denote posttreatment days (e.g., the day after the last dose will be Day +1).

Similarly, relative days for an event or measurement occurring before a reference date (generally the date of the first dose of study drug) are calculated as follows:

- Relative Day = (Event Date-Reference Date)

Relative days for an event or measurement occurring on or after the reference date to the last day of dose administration are calculated as follows:

- Relative Day = (Event Date-Reference Date) + 1

For events or measurements occurring after the date of last dose of study drug (as defined above), the relative day will be calculated with the date of last dose administration as reference. Relative day in this case will be prefixed with '+' in the data listings and will be calculated as follows:

- Relative Day = + (Event Date-Reference Date)

### **3.2.2.2 End of the 16-week treatment period**

The end of the 16-week overall treatment period will be either the date of Visit 7 for subjects completing the Treatment Period, or the date of the early discontinuation visit (EDV), for subjects who discontinued during the Treatment Period. If a subject does not have a Visit 7/EDV, then the date of the final contact will define the end date of the Treatment Period.

### **3.2.3 Analysis periods**

The start and end dates of each analysis period (following the study design) are used for the classification of efficacy and safety data. The exact start and end of each of these periods is described for calculation purposes in Table 3–1. Note that measurements obtained from diaries returned on the start date of the Titration and Stabilization Period would be included in the Baseline Period calculations. Refer to Section 3.3.1. Similarly, measurements from diaries returned on the start date of a subsequent period would be included in calculations for the previous period.

**Table 3–1: Start and end of EP0091 analysis periods**

Analysis Period			Details
Description	Start	End	
Baseline (Week -4)	Date of informed consent at Visit 1	Date of the day before the date of Visit 2.	This is an approximate 28-day period for calculation of Baseline seizure frequencies. Study drug is dispensed, and first dose is generally taken the day of the Baseline Visit (Visit 2, Day 1). Note the pre-dose assessments will also be included in the Baseline Period.
Titration and Stabilization*	The date of the Baseline Visit, (Visit 2, Day 1).	The date of the day before Visit 4 or the end of the treatment period if the subject has discontinued prior to Visit 4.	For evaluation purposes, if results are presented by analysis period, the Titration and the Stabilization interval will be considered together (approximately 4 weeks in total). Titration is a period of dose increases to reach the protocol specified dose. Stabilization is an approximate week-long interval to stabilize at the target dose level. During stabilization the dose may be adjusted once (i.e. to a fallback dose).
Maintenance*	The date of Visit 4.	The date of Visit 7 or the end of the treatment period if the subject has discontinued prior to Visit 7.	This is a 12-week period where the subject remains on the randomized target dose (or fallback dose, if applicable).
16-week Treatment Period*	The date of the Baseline visit (Visit 2)	The date of Visit 7 or the end of the treatment period if the subject has discontinued prior to Visit 7.	Titration and Stabilization Period and Maintenance Period combined.
Conversion	The date of the day after Visit 7	The date of Visit 8.	This is a 3-week period of dose conversion to enable the subjects to enroll into the OLE study EP0093.
Taper and Safety Follow-up	The date of the day after Visit 7/EDV or the date of day after Visit 8 if the subject tapered after conversion	The date of final contact.	Subjects who withdraw from the study or decide not to participate in the OLE study will be tapered off the IMP during a 3-week period followed by a 1-week drug-free period. A SFU visit will be performed 30 days after the last IMP intake.

OLE=open-label extension; SFU=Safety Follow Up

\* Only seizure data prior to and on the date of last dose of study medication will be included in the analysis.

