4.2.2 Other safety variables

Other safety variables are as follows:

- Incidence of TEAEs reported by the subject and/or caregiver or observed by the Investigator during the following periods: 16-week Treatment Period, 12-week Maintenance Period, 4-week Titration/Stabilization Period, and 3-week Taper Period
- Number of and reason for subjects requiring premature tapering due to TEAEs
- Number of and reason for subjects requiring a dose reduction during the Stabilization Period due to TEAEs
- Incidence of treatment-emergent SAEs during the following periods: 16-week Treatment Period, 12-week Maintenance Period, 4-week Titration/Stabilization Period
- Changes in clinical laboratory test parameters (including hematology, blood chemistry, and urinalysis)
- Changes in vital sign parameters (including pulse rate, systolic BP, diastolic BP, and respiratory rate)
- Changes in 12-lead ECG parameters
- Physical examination (including body weight) and neurological examination findings
- Changes in Psychiatric and Mental Status
- Occurrence of valvular abnormalities or pericardial effusion changes or other significant abnormalities as identified by 2-dimensional Doppler echocardiogram at each assessment by central reader
- Changes in withdrawal symptoms using Clinical Institute Withdrawal Assessment-Benzodiazepines (CIWA-B) from the End of Treatment Visit (Visit 7) to end of the Taper Period (Visit 8) and end of the SFU Period (Visit 9 [30 days after the last IMP intake]).

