7.2.2 Taper Period

The Taper Period, in case of withdrawal or completion of the study, will comprise 3 weeks as presented in Table 7-3. A faster or slower taper schedule than the suggested 3 weeks may be implemented if medically necessary, as per the Investigator's medical judgment. During the Taper Period, the dose of PSL must always be administered as bid morning and evening doses, approximately 12 hours apart. Concomitant AED dosages should be kept stable throughout the entire study including the Taper Period.

Subjects should be monitored during the Taper Period for withdrawal symptoms, including behavioral changes, withdrawal-related AEs or rebound seizures as well as the severity of the CIWA-B withdrawal scores. Withdrawal symptoms may require medical treatment for management of severe withdrawal symptoms. Additional AEDs (excluding prohibited medications) may be added and/or changes to dose regimens of concomitant AEDs are permitted if medically necessary as per Investigator's medical judgement to manage rebound seizures.

Table 7-3: Taper Period dosing

Dose Arm	Dose in mg per intake (morning-evening) during taper ^a				
	Week 16	Week 17		Week 18	
PSL 800mg/day	300-300	200-200	150-150	100-100	50-50
PSL 600mg/day					
PSL 400mg/day	200-200				
PSL 300mg/day	150-150	100-100		50-50	
PSL 200mg/day	100-100				
PSL 150mg/day	75-75				
PSL 100mg/day	50-50				
PSL 50mg/day	25-25				
Placebo	1-1				

PSL=padsevonil

^a Taper Period for subjects who choose an early discontinuation may occur before Week 16.

Note: Taper steps may vary in length by ±3 days per week.

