### **2.4.2 Other safety variables**

Other safety variables are as follows:

- Incidence of TEAEs reported by the subject and/or caregiver or observed by the Investigator during the following periods: 16-week Treatment Period, 12-week Maintenance Period, 4-week Titration/Stabilization Period, and 3-week Taper Period
- Number of and reason for subjects requiring premature tapering due to TEAEs
- Number of and reason for subjects requiring a dose reduction during the Stabilization Period due to TEAEs
- Incidence of treatment-emergent SAEs during the following periods: 16-week Treatment Period, 12-week Maintenance Period, 4-week Titration/Stabilization Period
- Changes in clinical laboratory test parameters (including hematology, blood chemistry, and urinalysis)
- Changes in vital sign parameters (including pulse rate, systolic BP, diastolic BP, and respiratory rate)
- Changes in 12-lead ECG parameters
- Physical examination (including body weight) and neurological examination findings

- Changes in Psychiatric and Mental Status
- Occurrence of valvular abnormalities or pericardial effusion changes or other significant abnormalities as identified by 2-dimensional Doppler echocardiogram at each assessment by central reader
- Changes in withdrawal symptoms using Clinical Institute Withdrawal Assessment-Benzodiazepines (CIWA-B) from the End of Treatment Visit (Visit 7) to end of the Taper Period (Visit 8) and end of the SFU Period (Visit 9 [30 days after the last IMP intake]).

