### **3.9 Changes to protocol-defined analyses**

Not applicable; there have not been any changed to protocol defined analyses.

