## 8 EFFICACY ANALYSES

Unless noted otherwise, analyses of efficacy endpoints will be performed on the FAS. Additional analyses of selected efficacy endpoints will be performed using the PPS as described in the sections below. For the efficacy variables described below, seizure frequency refers to a 28-day adjusted frequency; observable focal-onset seizures refer to Type IA1, IB, and IC (ILAE Classification of Epileptic Seizures, 1981); focal-onset seizures include all Type I seizures; and seizure-free status and seizure-free days include all seizure types (Types I, II, and III). Only seizure data prior to and on the date of last dose of study medication will be included in the analysis. Unless noted otherwise, all efficacy tables will be presented by treatment group.

As listed in Section 2.3.1, separate primary and secondary seizure frequency efficacy variables have been designated for submission to FDA and submission to European regulatory agencies along with other seizure frequency efficacy variables used for both submissions. A summary of seizure frequency variables and status as primary or secondary is presented in Table 8-1.

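### The SAP names adverse events in the 3-week Taper Period as a safety variable but tabulates only a merged taper and follow-up period, and it plans no entire-study table of serious events

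*SAP*

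**What the plan says.** **The variable.** Protocol 4.2.2 asks for TEAE incidence in four periods: "16-week Treatment Period, 12-week Maintenance Period, 4-week Titration/Stabilization Period, and 3-week Taper Period". SAP 2.4.2 repeats the list, ending "12-week Maintenance Period, 4-week Titration/Stabilization Period, and 3-week Taper Period".

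**The analysis period.** SAP Table 3–1 has one row, Taper and Safety Follow-up. Its start is "The date of the day after Visit 7/EDV or the date of day after Visit 8 if the subject tapered after conversion" and its end is "The date of final contact". The same row explains that these subjects "will be tapered off the IMP during a 3-week period followed by a 1-week drug-free period", with a safety follow-up visit 30 days after the last intake.

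**The planned tables.** SAP 10.2 gives TEAEs by period, with taper and safety follow-up as a single period. Serious TEAEs are tabulated for the Treatment, Titration and Stabilization, and Maintenance Periods only. Serious events by relationship and fatal events by relationship sit under the heading for the overall Treatment Period.

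**The primary safety variables.** Protocol 4.2.1 and SAP 2.4.1 include the incidence of treatment-emergent serious events over the whole study.

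**Declared changes.** SAP 3.9 reads: "Not applicable; there have not been any changed to protocol defined analyses".

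**The concern.** Followed exactly, the plan produces a quantity other than the one it names. An incidence over a window that runs on to final contact includes events while the dose is falling and events after the drug has gone. For a drug with benzodiazepine-site activity the timing of withdrawal events matters, and Protocol 7.2.2 treats it so: "Subjects should be monitored during the Taper Period for withdrawal symptoms, including behavioral changes, withdrawal-related AEs or rebound seizures". A reader of the merged table cannot tell the two intervals apart by arm.

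The serious-event gap concerns a primary safety variable. A serious event after Visit 7 would be counted among all TEAEs of its period, but no incidence table would show it as serious. This includes the Conversion Period, when subjects from the placebo arm first receive padsevonil.

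Because SAP 3.9 says nothing changed, neither departure is visible to someone checking the report against the protocol.

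**Working it through.** **1. Variables against planned tables**

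| Named variable | Where named | Planned in SAP 10.2 |
|---|---|---|
| TEAEs, 3-week Taper Period | Protocol 4.2.2, SAP 2.4.2 | Merged taper and follow-up period only |
| Serious TEAEs, entire study | Protocol 4.2.1, SAP 2.4.1 | Treatment Period and its two parts only |
| Serious TEAEs by treatment-phase period | Protocol 4.2.2, SAP 2.4.2 | As named |

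The first two rows do not match; the third does. SAP 10.2 opens with a general statement that TEAEs at any time in the study will be summarized, but it does not mention serious events and none of the tables listed after it is an entire-study serious table. SAP 5.1 classifies discontinuations due to adverse events by seriousness, which is disposition, not serious-event incidence.

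**2. The documents' own durations**

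Inputs: Baseline 4 weeks, Treatment 16 weeks, dose reduction 3 weeks, follow-up visit 30 days after last intake (Protocol 5.1, SAP 2.6.1).

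- Exposure: 16 + 3 = 19 weeks, as stated in Protocol 5.1.2.
- Total: 4 + 16 + 3 + 4 = 27 weeks, as stated (27.3 with a 30-day follow-up).

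The 19-week figure confirms that the 3 taper weeks are on drug, so the last dose falls at the end of the taper.

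**3. Composition of the merged window**

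- Length: 21 + 30 = 51 days.
- On falling doses: 21/51 = 41%.
- Off drug: 30/51 = 59%.

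**4. Sensitivity to definitions**

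- Protocol 5.1 also describes a 4-week Taper Period, made of 3 weeks of dose reduction and a drug-free week. On that definition the share is 28/51 = 55%.
- The end is final contact, and serious-event reporting runs to the 6-month (±1 month) echocardiogram. If final contact were that late (an assumption, at 30.4 days per month), the share would be 21/(21 + 30.4 × m): 12% at m = 5, 10% at m = 6 and 9% at m = 7.
- Taper may be faster or slower at the investigator's judgement, so individual shares vary.

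On none of these readings is the merged window the named period.

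**The case against.** The strongest reply is that nothing is lost. The last-dose date is recorded (SAP 10.1), the adverse event listing shows the daily dose at onset, and CRF data are listed in general (SAP 3.1). On-taper and off-drug events can therefore be separated subject by subject. This stands against any claim that the taper cannot be reported. It does not supply the incidence by arm that both documents name.

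A second reply is that withdrawal is covered elsewhere. Benzodiazepine withdrawal scores (CIWA-B) are summarized at Visits 7, 8 and 9, psychiatric and mental status is summarized by visit, and conversion is kept apart from taper. This also stands in part. However, Visit 7 is the start of the taper and Visit 8 is a week after the last intake, so no withdrawal score is scheduled while the dose is falling.

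A third is that Protocol 4.2.2 asks for serious events by treatment-phase period only. That is correct: serious TEAEs split by taper and post-treatment go beyond the protocol. The entire-study serious table does not, since it is a named primary safety variable.

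A reader might also infer that the SAP discards rebound seizures, because SAP 8 says "Only seizure data prior to and on the date of last dose of study medication will be included in the analysis". The documents do not support this. The matching footnote in Table 3–1 marks only the three treatment-phase rows. SAP 10.1 takes the overall last dose from the termination form, which for a tapering subject is the end of the taper, so the rule removes no on-taper diary day. Taper seizures go unsummarized because SAP 8.3.2.23 covers only the treatment-phase periods and neither document names rebound seizure frequency as a variable. Seizure worsening judged clinically significant is recorded as an adverse event and reaches the merged TEAE table.

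**Conclusion.** The point holds as a mismatch between named variables and planned tables. One listed safety variable, TEAEs in the 3-week Taper Period, has no matching analysis period or table, and the change is undeclared. One primary safety variable, serious treatment-emergent events over the entire study, has tables only within the Treatment Period.

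On nominal lengths the named taper is 41% of the window that replaces it (55% if the drug-free week is counted as taper, 9% to 12% if final contact is the late echocardiogram). The 41% assumes a 21-day taper and final contact at 30 days.

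The stronger readings, that these events cannot be reported or that withdrawal goes undescribed, fail: the dates exist and partial summaries are planned. The matter is descriptive safety reporting and touches no efficacy conclusion, but it should be corrected because the SAP contradicts its own variable list.

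**What to change.** - Split the Table 3–1 row at the date of last intake. **Taper** runs from the day after Visit 7 or early discontinuation (after Visit 8 if tapering after conversion) to the last dose. **Post-treatment** runs from the day after the last dose to final contact.
- State that the drug-free week, which Protocol 5.1 places inside its 4-week Taper Period, is assigned to Post-treatment for analysis.
- In SAP 10.2, tabulate TEAEs and serious TEAEs for each of the two periods, and add an entire-study serious TEAE table. Note on that table that placebo-arm subjects who convert receive padsevonil after Visit 7.
- If the merged period is kept, declare it in SAP 3.9 as a change from the protocol-defined variable.
- Optionally, add a descriptive seizure-frequency summary after Visit 7, since the diary continues to Visit 9. This would be a new analysis, and the concomitant antiepileptic changes permitted during taper would confound it.

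The cost is SAP wording and about four more tables: one from the TEAE split, two for serious TEAEs by part, and one for the entire study. All use data already collected. The limitation is that tapering subjects are self-selected, so the tables are descriptive and comparisons between arms should be read with that in mind.
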